#### 9.1.1.2 Serious Adverse Event

A SAE is any untoward medical occurrence that at any dose:

- o Results in death
- Is life-threatening (defined as an event in which the patient was at immediate risk of death at the time of the event; it does not refer to an event that hypothetically might have caused it if it was more severe)
- Requires patient hospitalization or prolongation of existing hospitalization
- Results in persistent or significant disability/incapacity (The disability is a substantial disruption of a person's ability to conduct normal life functions)
- o Is a congenital anomaly or birth defect
- o Is an important medical event which is defined as a medical event that may not be immediately life-threatening or result in death or hospitalization but may jeopardize the patient or may require intervention (i.e., specific measures or corrective treatment) to prevent one of the other outcomes listed above and which should also usually be considered serious

#### CONFIDENTIAL

Release date: Edition number

MOD-3783

12 August 2016

GED version

Examples of such events include, but are not limited to, intensive treatment in an emergency room or at home for allergic bronchospasm; blood dyscrasia (e.g., agranulocytosis, aplastic anemia, bone marrow aplasia, myelodysplasia, pancytopenia, etc.) or convulsions (seizures, epilepsy, epileptic fit, absence, etc.); ALT > 3 x ULN + total bilirubin > 2 x ULN or asymptomatic ALT increase < 10 x ULN; relapse of a previous malignancy or second primary malignancy.

Suspected transmission of an infectious agent (e.g. pathogenic or non-pathogenic) via the study drug is considered a SAE.

Although pregnancy, overdose or cancer, are not always serious by regulatory definition, these events must be handled as SAEs.

Any event or hospitalization that is unequivocally due to relapse of disease must not be reported as a SAE.

## NOTE:

The following hospitalizations are not considered SAEs in Innate Pharma clinical studies:

- A visit to the emergency room or other hospital department < 24 hours, that does not result in admission (unless considered an important medical or life-threatening event)
- Elective surgery or procedure (e.g. stent), planned prior to signing consent
- o Admissions as per protocol for a planned medical/surgical procedure
- Routine health assessment requiring admission for baseline/trending of health status (e.g., routine colonoscopy)
- Medical/surgical admission other than remedying ill health state and planned prior to entry into the study. Appropriate documentation is required in these cases
- Admission for another life circumstance that carries no bearing on health status and requires no medical/surgical intervention (e.g., lack of housing, economic inadequacy, care-giver respite, family circumstances, administrative)

Disease relapse/progression is not considered as a SAE in this study.

#### 9.1.1.3 Unexpected Adverse Drug Reaction

An unexpected adverse drug reaction is defined (as per ICH Topic E2A) as an adverse reaction which nature or severity is not consistent with the relevant source document (Investigator's Brochure for IPH2201). When reported as serious, the unexpected adverse reaction is defined as Suspected Unexpected Serious Adverse Reaction (SUSAR).

#### 9.1.1.4 Determination of relatedness

The Investigator will use medical consideration to determine the relatedness of an AE with the study drug based on the following definitions:

#### Not Related

This category applies to AEs that are due to extraneous causes (disease, concomitant medication, environment, etc.) and are not related to the administration of study drug.

#### Probably Not Related (must have first two criteria below)

This category applies to AEs that are unlikely related to the administration of the study drug. The relationship of an AE to the study drug can be considered probably not related if:

- The AE does not follow a reasonable temporal sequence from administration of the drug
- The AE could readily have been a result of the patient's clinical state or other underlying medical condition, environmental or toxic factors, or other modes of therapy administered to the patient
- The AE does not follow a known response pattern to the suspected drug
- The AE does not reappear or worsen when the Study Drug is re-administered

#### CONFIDENTIAL

Release date: Edition number

GED version

#### Possibly Related (must have first two criteria below)

This category applies to AEs that are unlikely to be related to the administration of the study drug, but the possibility cannot be ruled-out with certainty. The relationship of an AE to the study drug can be considered possibly related if:

- The AE follows a reasonable temporal sequence from administration of the study drug
- The AE could readily have been a result of the patient's clinical state, environmental or toxic factors, or other modes of therapy administered to the patient
- The AE follows a known response pattern to the suspected Study Drug

#### o Probably Related (must have first three criteria below)

This category applies to AEs that are considered with a high degree of certainty to be related to the administration of the study drug. The relationship of an AE to the study drug can be considered probably related if:

- The AE follows a reasonable temporal sequence from administration of the study drug
- The AE could not be reasonably explained by the known characteristics of the patient's clinical state, environmental or toxic factors, or other modes of therapy administered to the patient
- The AE disappears or decreases upon cessation of study drug or reduction in dose
- The AE follows a known response pattern to the suspected study drug

#### o Definitely Related (must have first three criteria below)

This category applies to AEs that are determined with certainty to be related to the administration of the study drug. The relationship of an AE to the study drug can be considered definitely related if:

- The AE follows a reasonable temporal sequence from administration of the study drug or study drug levels have been established in body fluids or tissues
- The AE could not be reasonably explained by the known characteristics of the patient's clinical state, environmental or toxic factors, or other modes of therapy administered to the patient;
- The AE disappears or decreases upon cessation of study drug or reduction in dose and, if applicable, appears upon rechallenge
- The AE follows a known response pattern to the suspected Study Drug
- There are exceptions when an AE does not disappear upon discontinuation of the study drug, yet study drug relatedness clearly exists; e.g., 1) tardive dyskinesia, 2) fixed drug eruptions

#### 9.1.1.5 Death

All deaths that occur during the study period must be reported.

Death as a result of disease progression is not considered as AE/SAEs. Death as a result of other disease is not considered as (S)AE but the disease which led to the death must be considered as a (S)AE. However, death must be collected on the appropriate eCRF form. The site should continue to follow all subjects for survival and collect information around the death on the appropriate eCRF form until the end of the trial.

Release date: Edition number

GED version

# 9.1.2 Adverse Events Collection and Reporting

All AEs and SAEs, whether related or not related to study drug, including those thought to be associated with protocol-specified procedures, must be collected throughout the study from the time of patient signing the consent form until the end of study visit, or until the patient's last study visit. All reported AEs and SAEs will be followed until resolution. The Investigator should take appropriate measures to follow all AEs until clinical recovery is complete and laboratory results have returned to normal, or until progression has been stabilized, or until death, in order to ensure the safety of the patients. This may imply that observations will continue beyond the last planned visit per protocol, and that additional investigations may be requested by the monitoring team up to as noticed by the Sponsor. When treatment is prematurely discontinued, the patient's observations will continue until the end of the study as defined by the protocol for that patient.

All AEs will be recorded on the eCRFs. The records will describe the nature (diagnosis or single syndrome as much as possible, alternatively signs and symptoms) severity, using the NCI CTCAE term (version 4.3 of June 14, 2010), date/time of onset, date/time of end, actions taken with respect to IMP, corrective treatment/therapy given, additional investigations performed, outcome, and causality (relationship to study treatment according to the investigator's assessment).

It will be specified whether the event is serious or not according to the definition of SAE (See section 9.1.1).

A sponsor safety representative will determine the causal relationship when it is not clearly provided by the investigator.

Laboratory, vital signs or ECG abnormalities are to be recorded as AEs only if:

- o Symptomatic and/or
- Requiring either corrective treatment or consultation, and/or
- Leading to IMP discontinuation or modification of dosing, and/or
- Fulfilling a seriousness criterion

# 9.1.2.1 Follow-up and Handling of unresolved AE/SAEs at completion/withdrawal

Ongoing adverse events should be reviewed at each subsequent assessment. If resolved, the details should be recorded in the eCRF. If any AE changes for the worse in frequency of attacks/symptoms or in severity, a new record of the event must be started (i.e. distinct reports are required for differing frequencies and/or severity of the same event to enable comprehensive safety reports and later analysis).

All non-serious AEs must be followed until the outcome of the event is "recovering" (for chronic conditions) or recovered, or until the patient's last study visit and until all queries related to these AEs have been resolved.

If the patient dies from another event, these cases can be closed with an outcome "not recovered".

All AEs and SAEs must be followed until resolution or stabilization.

#### 9.1.3 Serious Adverse Events Reporting

Any other AE not listed as an expected event in the Investigator's Brochure or in this protocol will be considered unexpected.

Investigators and other site personnel must report all SAEs within 24 hours of becoming aware of a SAE to Medpace (see as below).

SAEs must be reported within 24 hours (immediately but no later than the end of the next business day), regardless of the time that may have elapsed since the time the event occurred, and regardless of the causal relationship of the investigational medicinal product to the event.

#### CONFIDENTIAL

Release date: Edition number

MOD-3783

12 August 2016

GED version

All SAEs should be reported on an SAE form (initial report), which should be completed by the investigator/other relevant site staff, signed by the investigator and faxed to Medpace (see as below). In addition, SAEs should be reported on the adverse event eCRF page.

The investigator will be requested to supply as much detailed information regarding the event as is available at the time of the initial contact.

ANY SERIOUS ADVERSE EVENTS, WHETHER OR NOT RELATED TO THE STUDY DRUG, MUST BE REPORTED IMMEDIATELY TO:

The investigator must immediately or as soon as possible send (preferably by fax or e-mail) a photocopy of all examinations carried out and the dates on which these examinations were performed, to Pharmacovigilance.

In addition, care should be taken to ensure that the patient's identity is protected and the patient's identifiers in the clinical trial are properly mentioned on any copy of a source document provided to the Sponsor. For laboratory results, the investigator must include the laboratory normal ranges.

A back-up plan (using a paper CRF process) is available and should be used when the e CRF system does not work.

# 9.1.3.1 Follow-up of Serious Adverse Events

Follow-up information on SAEs must also be reported by the investigator within the same time frames.

A follow-up report to an SAE should be prepared if any relevant change in the condition of the patient occurs after the initial report, or any new relevant information becomes available.

The follow-up report should be supplied on an SAE report form and clearly labeled as 'follow-up'. Follow-up forms should contain only essential patient and event identifying data and all new data; there should be no repetition of any data given in the initial report.

All SAEs will be followed up until the outcome of this event is recovered, recovered with sequelae or fatal and until all queries have been resolved.

For cases of chronic conditions or if the patient dies from another event, these cases can be close with an outcome of "recovering" or "not recovered".

All SAEs have to be reported, whether or not considered causally related to the investigational product or to the study procedure(s).

Any SAE brought to the attention and assessed to and by the Investigator, occurring at any time after the end of the study visit and that may be related with a reasonable possibility to the study treatment, as assessed by the investigator, should also be notified to the monitoring team.

#### 9.1.4 Abnormal laboratory values/vital signs

The reporting of laboratory / vital signs / ECG abnormalities as laboratory findings / vital signs / ECG and as AEs should be avoided. They should not be reported as AEs (using the NCI CTCAE version 4.3 of June 14, 2010 terminology) unless any one of the following are met:

- o Any criterion for a SAE is fulfilled
- The laboratory / vital signs / ECG abnormality causes the subject to discontinue from the study treatment

Release date: Edition number

MOD-3783

12 August 2016

GED version

- The laboratory / vital signs / ECG abnormality causes the subject to interrupt the study treatment
- The laboratory / vital signs / ECG abnormality requires intervention as corrective treatment or consultation and/or
- Symptomatic and/or
- o The Investigator believes that the abnormality should be reported as an AE

All laboratory tests for which abnormal results are collected after the initiation of study treatment should be repeated until the values return to normal or to a stable status. Abnormal results are defined as those falling out of the normal laboratory range and that are clinically significant. The frequency with which such checks should be made will be defined by the investigator's opinion depending on the degree of abnormality.

#### 9.1.5 Overdose

An overdose is defined as the accidental or intentional ingestion or infusion of any dose of a product that is considered both excessive and medically significant.

All symptoms associated with the overdose should be reported as SAEs.

# 9.1.6 Pregnancy Reporting

If the subject or partner of a subject participating in the study becomes pregnant during the study or within 5 months of discontinuing study medication, the investigator should report the pregnancy to Medpace Clinical Safety within 24 hours of being notified. Medpace Clinical Safety will then forward the Exposure In Utero form to the investigator for completion.

A patient becoming pregnant while on IMP will immediately be withdrawn from the study and early termination study procedures will be performed

The subject or partner should be followed by the investigator until completion of the pregnancy. If the pregnancy ends for any reason before the anticipated date, the investigator should notify Medpace Clinical Safety. At the completion of the pregnancy, the investigator will document the outcome of the pregnancy. If the outcome of the pregnancy meets criteria for immediate classification as a SAE (i.e., postpartum complication, spontaneous abortion, stillbirth, neonatal death, or congenital anomaly), the investigator should follow the procedures for reporting as SAE.

#### 9.1.7 Drug Induced Liver Injury (DILI)

Potential drug induced liver injury (DILI) is considered an important medical event. Although they are not always serious by regulatory definition, these events must be handled as SAEs.

Wherever possible, timely confirmation within 48-72 hours of initial liver-related laboratory abnormalities should occur prior to the reporting of a potential DILI event. All occurrences of potential DILIs, meeting the defined criteria, must be reported as SAEs.

Potential drug induced liver injury is defined as:

1. AT (ALT or AST) elevation > 3 times upper limit of normal (ULN)

AND

2. Total bilirubin > 2 times ULN, without initial findings of cholestasis (elevated serum alkaline phosphatase)

AND

#### CONFIDENTIAL

Release date: Edition number

MOD-3783

12 August 2016

GED version

 No cholestatic or other immediately apparent possible causes of AT elevation and hyperbilirubinemia, including, but not limited to, viral hepatitis, pre-existing chronic or acute liver disease, or the administration of other drug(s) known to be hepatotoxic

# 9.1.8 Reporting to Competent Authorities and Ethics Committees

Investigator Brochure will be the reference document for safety assessment.

Innate Pharma is responsible for notifying SUSARs to health authorities in accordance with local regulations.

The investigator is responsible for informing the Institutional Review Board (IRB) in a timely manner and in accordance with local procedures.

# 9.2 SAFETY ASSESSMENTS

Subjects will be considered evaluable for safety if they have received any dose of the study drug. Toxicity assessments will be continuous during the Treatment period and the Clinical Follow-up periods.

# 9.2.1 Clinical Safety

The following assessments will allow the safety evaluation of the treatment according to the study flow chart:

- o Full physical examination,
- Vital signs (Systolic and Diastolic Blood Pressure, Orthostatic Response, Heart Rate, Height, Weight)
  - Determination of the reference arm for blood pressure (BP) measurements: At first visit after the patient has rested comfortably for at least 10 minutes, BP is measured on both of the patient's arms while the patient is in sitting position and then again after two minutes on both arms. The arm with the higher diastolic BP will be determined at this visit, identifying the reference arm for future measurement throughout the study. The highest value will be recorded in the e-CRF (all BP values are to be recorded in the source data) as the BP to determine the reference arm. An additional measurement may be made to determine the screening BP
  - BP at all subsequent visits should be measured when the patient is quiet and seated and with their determined reference arm outstretched in line with mid-sternum and supported. Measurement at all subsequent visit should be taken under standardized conditions, approximately at the same time of the day, on the reference arm, with the same device (after the patient has rested comfortably for at least five minutes) and the values are to be recorded in the e-CRF. Both systolic blood pressure (SBP) and diastolic blood pressure (DBP) should be recorded
  - Heart rate will be measured at the time of the BP measurement
  - Height will be measured at screening visit when the patient's shoes are off, feet together
    and arms by the sides. Heels, buttocks and upper back should also be in contact with the
    wall when the measurement is made

#### CONFIDENTIAL

Release date: Edition number

MOD-3783

12 August 2016

GED version

Body weight should be obtained at screening visit and at end of treatment, with the patient wearing undergarments or very light clothing and no shoes, and with an empty bladder. The floor surface on which the scale rests must be hard and should not be carpeted or covered with other soft material. The same scale should be used throughout the study, and calibrated on a regular basis as recommended by the manufacturer. The weight is read and recorded in the e-CRF and Source Data. Self-reported weights are not

- o Collection of AEs
- o 12 lead ECG standard. The ECG machine should compute the heart rate, PR, QT and QTC (calculated using Bazett's formula), QRS duration. The investigator or a cardiologist will evaluate the ECG. ECGs which are assessed by them as "abnormal, clinically significant", should be reported as AEs. A standard copy of each anonymized ECG should be archived by the sponsor of the study

acceptable and patients must not read the scales themselves

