### PHASE I flow chart foot notes:

- 1 IPH2201 administration should be performed 14 days ± 3 days after previous administration from W0 to W6. Starting from W8, IPH2201 administration should be performed 28 days +/-7 days after previous administration.
- 2 Ibrutinib will be administered at the dose of 420 mg (three 140 mg capsules) orally once daily.
- 3 Screening visit must be performed 3 weeks maximum prior to W0 visit;
- 4 Full physical exam at baseline; focused on symptoms and any new findings at all subsequent visits
- Hematology: red blood cell(s) (RBC), WBC with differential count, platelets, hemoglobin; mean Corpuscular Volume (MCV), hematocrit. All visits, pre-dose. Additional samplings at W0 H0+4. W2 H0+4. W4 H0+4 and W6 H0+4.
- Biochemistry: sodium, potassium, chloride, bicarbonate, calcium, magnesium, phosphate, total proteins, and albumin, urea, uric acid, creatinine, calculated creatinine clearance, ALP, total bilirubin, LDH, AST (SGOT), ALT (SGPT), gamma glutamyl transferase (GGT), amylase, lipase, glucose, C-reactive protein (CRP), and fibrinogen. At every visit from screening until W12, then every 2 months, at W24, at W32, W40, W48; at EOT, FU3, FU5, FU6, FU7 and EOS. At W0 H0+4, W2 H0+4, W4 H0+4 and W6 H0+4 additional samplings are required.
- 7 Thyroid: TSH, free T3 and free T4

16

- 8 Coagulation factors: activated partial thromboplastin time (APTT), prothrombin time (PT). at Screening, at predose of W4 and W8, and at EOT
- 9 EOT visit to be performed in case of premature discontinuation or 14 days +3 days after W52 visit.
- 10 Urinalysis: PH, Glucose, Leucocytes, proteins, blood and hemoglobin, to be performed at screening, in predose of W4 and W32 visits and at EOT
- 11 12-lead ECG should be performed at screening, W0 predose, W0 H0+3 +/- 1 hour, in predose of W6, W16, W32 visits and at EOS
- 12 End of study visit to be performed in case of premature discontinuation, or at the end of the follow up, +/- 7 days after previous visit
- 13 Testing for IgG, IgM, IgA and total immunoglobulin levels at screening, in predose of W16 and W32 visits and at EOT.

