#### CONFIDENTIAL

Release date: Edition number

GED version

MOD-3783

12 August 2016

10. Abnormal cardiac status with any of the following:

- Unstable angina
- o Myocardial infarction within the last 6 months
- o Arrhythmia requiring treatment and which is not stabilized by the treatment
- QTc > 500ms (Bazett)
- o History of documented congestive heart failure (New York Heart Association functional classification III-IV)
- 11. Pregnant women are excluded from this study; breastfeeding should be discontinued
- 12. Current active infectious disease or positive serology for HIV and/or positive PCR for HCV, or chronic HBV infection (positive Hbs Aq, and in patients treated by IVIG, a positive HBV PCR)
- 13. History of another malignancy within 3 years, except a malignancy, which in the opinion of the investigator is inactive and would not limit survival to less than 5 years
- 14. History of allogeneic stem cell or solid organ transplantation
- 15. Intermittent or continuous renal replacement therapy
- 16. Concomitant treatment with other investigational agents
- 17. Systemic treatment with steroids or other immunosuppressive agents within 30 days prior to entry, but physiological replacement with hydrocortisone or equivalent is acceptable
- 18. Patients who are on chronic treatment with strong or moderate CYP3A4 inhibitors (e.g., nefazodone, aprepitant, ciprofloxacin, diltiazem, erythromycin, fluconazole, grapefruit juice, imatinib, verapamil) or inducers (e.g., carbamazepine, rifampin, phenytoin and St. John's Wort) should be excluded from study entry (see Appendix V)
- 19. Patients should not have psychological, familial, sociological, or geographical conditions that do not permit medical follow-up and compliance with study protocol

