9.6 Vital Signs, Physical Findings and Other Observations Related to Safety

[figure not shown]
Descriptive statistics of ECOG results will be presented by a shift table, comparing the worst value over the study versus baseline.

Descriptive statistics of ECGs results (normal, abnormal not clinically significant, abnormal clinically significant), heart rate, PR interval, QT interval, Bazzett's QTc and QRS duration will be presented by visit. For the continuous parameters, both absolute values and change from baseline will be presented. Unscheduled visits will not be taken into account.

Data from vital signs and physical examination will only be listed.

10. References

- [2] Fleming T. One sample multiple testing procedure for phase II clinical trials. Biometrics 1982;38:143-151.
- [3] Common Terminology Criteria for Adverse Events (CTCAE) Version 4.03, dd. June 14, 2010 National Cancer Institute

TPL N°: eTPL SA-02-01 TPL Version: 02 Of SOP SA-02.08

TPL N°: eTPL SA-02-01 TPL Version: 02

Of SOP SA-02.08
TPL Effective Date: 31 Mar 2016
Approved in Vault: 3/8/2019

[figure not shown]
Confidential	

TPL N°: eTPL SA-02-01 Of SOP SA-02.08 TPL Effective Date: 31 Mar 2016 TPL Version: 02

Approved in Vault: 3/8/2019

Innate - IPH2201-202

Version: 2.0

Page 26 of 26

TPL N°: eTPL SA-02-01 Of SOP SA-02.08 TPL Effective Date: 31 Mar 2016 TPL Version: 02

Approved in Vault: 3/8/2019

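### QTc is computed and summarised by Bazett's formula alone, so its change from baseline carries a heart-rate term unless the QT-RR exponent is exactly 0.5; a cube-root QTc row beside it is a free improvement

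*Protocol*

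**What the plan says.** Protocol 9.2.1 (Clinical Safety) sets out what is read from each tracing: "The ECG machine should compute the heart rate, PR, QT and QTC (calculated using Bazett's formula"; QRS duration is computed as well. The investigator or a cardiologist evaluates each ECG, and one judged abnormal and clinically significant is to be reported as an adverse event.

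The footnotes to both flow charts give the same ECG times. For phase Ib: "12-lead ECG should be performed at screening, W0 predose, W0 H0+3 +/- 1 hour", then before dosing at W6, W16 and W32, and at the end-of-study visit.

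SAP 9.6 summarises the normal/abnormal classification together with the measured intervals: "heart rate, PR interval, QT interval, Bazzett's QTc and QRS duration will be presented by visit". It adds: "For the continuous parameters, both absolute values and change from baseline will be presented". SAP 4.1 presents phase Ib tables by dose level and overall, and promises listings of individual values for everything tabulated.

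Exclusion criterion 10 (Protocol 4.2) also uses Bazett's QTc, with a limit of 500 ms. Neither document names another correction, a QTc analysis adjusted for heart rate, or categorical QTc limits for the tables.

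**The concern.** A QT correction is meant to make values taken at different heart rates comparable. Bazett's square-root formula does so only if QT is proportional to RR to the power 0.5. If the exponent is smaller, a rise in heart rate appears as QTc prolongation, and a fall in heart rate subtracts from any real prolongation.

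Heart rate could move in this trial. An ECG is taken before the first infusion and again about two hours after it ends, and the protocol anticipates infusion-related events. Protocol 1.1.2 describes anaemia and infection as part of CLL, and the CR definition in 7.1 requires haemoglobin above 11 g/dl and no constitutional symptoms. Responding patients may therefore change in ways that lower heart rate. For a safety table the second direction, a real effect partly hidden, is the less comfortable one.

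ECG results are part of the safety assessment in both phases (Protocol 3.1.1 and 3.1.2). There is no control arm to show how much of a QTc change follows heart rate alone.

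**Working it through.** **Plan's own figure.** The documents state no figure for QTc, so there is nothing to reproduce. The phase IIa decision rule (at least 4 CRs in 27 patients, SAP 3.3.2) does not enter.

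**Inputs from the documents.** Bazett is the only correction (Protocol 9.2.1, SAP 9.6). Heart rate and QT are recorded on each ECG (Protocol 9.2.1). Absolute value and change from baseline are tabulated (SAP 9.6).

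**Assumed inputs.** QT is 400 ms at 60 bpm. The QT-RR exponent *b* is varied from 0.25 to 0.50. Baseline heart rate is 70 bpm. Only heart rate changes; repolarisation does not.

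**Formulas**, with RR = 60/HR in seconds:

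- QT = 400 × (60/HR)^b
- Bazett: QTcB = QT / (60/HR)^(1/2) = 400 × (HR/60)^(1/2 − b)
- Cube-root (Fridericia): QTcF = QT / (60/HR)^(1/3) = 400 × (HR/60)^(1/3 − b)

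For any tracing it follows that QTcB = QTcF × (HR/60)^(1/6). The two agree only at 60 bpm. QTcB is free of heart rate only at *b* = 1/2, and QTcF only at *b* = 1/3.

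**One case in full**, *b* = 1/3, from 70 to 80 bpm:

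- QTcB at 70 = 400 × (70/60)^(1/6) = 410.4 ms
- QTcB at 80 = 400 × (80/60)^(1/6) = 419.6 ms
- Bazett change = +9.2 ms; cube-root change = 0.0 ms

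**Spurious change from baseline (ms), starting at 70 bpm:**

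| Heart rate goes to | Correction | b = 0.25 | b = 0.333 | b = 0.40 | b = 0.50 |
|---|---|---|---|---|---|
| 80 bpm | Bazett | +14.1 | +9.2 | +5.5 | 0.0 |
| 80 bpm | Cube-root | +4.5 | 0.0 | -3.5 | -8.6 |
| 60 bpm | Bazett | -15.7 | -10.4 | -6.2 | 0.0 |
| 60 bpm | Cube-root | -5.2 | 0.0 | +4.1 | +10.1 |
| 90 bpm | Bazett | +27.0 | +17.6 | +10.3 | 0.0 |
| 90 bpm | Cube-root | +8.6 | 0.0 | -6.6 | -16.0 |

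**Reading the table.** Neither formula is free of heart rate across the range. To first order the artefact is proportional to the distance of *b* from 1/2 (Bazett) or from 1/3 (cube-root). The two are therefore about equal in size at the midpoint, (1/2 + 1/3)/2 = 0.417. Below that the cube-root artefact is the smaller; above it, Bazett's is.

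For *b* between 1/3 and 1/2, the two artefacts have opposite signs or one is zero, so the pair brackets the true change of zero. At *b* = 0.25 both have the same sign and there is no bracket. This is why the two rows are more informative together, next to the heart-rate change, than either is alone.

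**The case against.** The strongest reply is that the same SAP sentence that tabulates Bazett's QTc also tabulates heart rate and uncorrected QT by visit, with changes from baseline, and that SAP 4.1 promises individual listings. A mean heart-rate shift is therefore visible, and anyone can derive another correction afterwards. This stands as mitigation. It does not take the heart-rate term out of the tabulated QTc changes, because separate by-visit means of heart rate and QT do not correct each patient's value.

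It is also fair that Bazett is prespecified consistently in eligibility, ECG acquisition and the SAP; that Protocol 10.1 calls the analyses descriptive; and that individual ECG findings are judged tracing by tracing, not from the tables. All of this stands and limits the importance of the point.

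Several stronger readings are tempting, and the documents do not support them:

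- A reader might infer that QT and heart rate are collected in order to avoid this problem. The documents state no such purpose; the data simply make another correction possible.
- A reader might infer that the cube-root value is the correct one and should replace Bazett's as the main summary. That needs a known exponent near 1/3, which the documents do not give. At 0.50 the cube-root value is the biased one.
- A reader might treat a heart-rate shift as established. It is plausible, but neither document reports heart-rate data.
- A reader might say that change from baseline is the only QTc comparison, or that cohorts of 3 to 6 patients are the reason the artefact persists. SAP 9.6 also gives absolute values and normal/abnormal categories, and a systematic heart-rate effect would not average out at any sample size.

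**Conclusion.** The point holds as a free improvement of minor importance. Bazett's is the only QT correction in the plan. Unless the QT-RR exponent is exactly 0.5, the tabulated QTc change from baseline mixes a heart-rate term with any repolarisation effect.

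For exponents from 0.25 to 0.40, a 10 bpm rise from 70 bpm adds about 5 to 14 ms, and a 10 bpm fall subtracts about 6 to 16 ms, with no repolarisation change. At 0.50 the artefact is zero. These figures rest on the assumed 400 ms at 60 bpm, the assumed exponents and the assumed heart-rate shifts.

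The plan has no QTc hypothesis. No dose-escalation, DLT or efficacy rule depends on these tables, and the CR analysis is untouched. The documents do not show that any conclusion of the trial would change.

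**What to change.** In SAP 9.6, add a derived variable QTcF = QT / (60/heart rate)^(1/3), calculated per tracing from the recorded QT (ms) and heart rate (bpm). Present it by visit, as absolute value and change from baseline, in a row beside Bazett's QTc. State that the two rows are to be read together with the heart-rate change, since neither correction is free of heart rate at every exponent.

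Keep Bazett's QTc in the tables, and leave the Bazett-based eligibility criterion unchanged.

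The cost is one derived variable and one extra table row. No new ECGs, data entry or protocol procedures are needed.
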